### **Reasons for SVR24 Non-Response**

Subjects who do not achieve SVR24 (SVR24 non-responders) will be categorized as having:

1. On-treatment virologic failure (see **On-treatment virologic failure** definition, if a subject meets both definitions of **Breakthrough** and **EOT failure**, he or she will be categorized as **Breakthrough** only);
2. HCV reinfection (see definition described earlier);

3. Relapse12 (see **Relapse12** definition);
4. Relapsed after achieving SVR12 (see **Relapse24** definition);
5. Prematurely discontinued study drug with no on-treatment virologic failure and no relapse after achieving SVR12 (defined as any SVR24 non-responder who prematurely discontinued study drug [study drug duration < 52 days for subjects assigned to 8 weeks of treatment, and < 77 days for subjects extended to 12 weeks of treatment] and did not meet the **On-treatment virologic failure** or **Relapse24** definitions);
6. Missing follow-up data in the SVR24 window (defined as any subject who completed study drug without data in the SVR24 window after applying the imputation rules and not meeting the definitions of [1], [2], [3], [4], or [5]);
7. Other (defined as any SVR24 non-responder not meeting the definitions of [1] – [6]).

For the reasons for SVR12/SVR24 nonresponse defined above, subjects are only to be counted in 1 category. For example, the categories of premature discontinuation and reinfection are mutually exclusive. Thus, subjects who are SVR12/SVR24 nonresponders meeting the definition of HCV reinfection are counted in the reinfection category and not to be counted in any other category (as in the example, even if such a subject who was determined to be a case of reinfection appeared to meet the definition of prematurely discontinued study drug with no on-treatment virologic failure, the subject is to be counted in the reinfection category only).

## 10.2 Handling of Multiplicity

In order to control the Type I error rate at 0.05, a fixed sequence testing procedure will be used for the two primary and two key secondary efficacy analyses of SVR12 as listed below. The fixed-sequence testing procedure will utilize the efficacy endpoint sequence of the first primary analysis followed by the second primary analysis, then the first key secondary analysis, and lastly the second key secondary analysis. For example, only if

success has been demonstrated for the first primary efficacy analysis of SVR12 based on the PP population in HCV GT 1, 2, 4, 5 and 6-infected subjects will the testing proceed to the second primary efficacy analysis of SVR12 based on the ITT population in HCV GT 1, 2, 4, 5 and 6-infected subjects. And only if success has been demonstrated for the second primary efficacy analysis of SVR12 will the testing proceed to the first key secondary efficacy analysis of SVR12 based on the PP population in HCV GT 1 - 6-infected subjects, and so on.

The multiplicity controlled efficacy analyses will be tested sequentially in the following order:

1. Primary 1: Efficacy of the SVR12 rate of 8-week treatment duration compared to the historical 12 week treatment duration based on the PP population in HCV GT 1, 2, 4, 5 and 6-infected subjects: If this endpoint is statistically significant, then proceed to the following efficacy endpoint. If this endpoint is not statistically significant then stop the testing procedure and declare that no endpoints in the study met statistical significance.
2. Primary 2: Efficacy of the SVR12 rate of 8-week treatment duration compared to the historical 12 week treatment duration based on ITT population in HCV GT 1, 2, 4, 5 or 6-infected subjects: If this endpoint is statistically significant, then declare the SVR12 endpoint is statistically significant on both PP and ITT population in HCV GT 1, 2, 4, 5 or 6-infected subjects. If not, then announce that SVR12 endpoint is statistically significant based on only the PP population in HCV GT 1, 2, 4, 5 or 6-infected subjects and stop testing.
3. Key Secondary 1: Efficacy of the SVR12 rate of 8-week treatment duration compared to the historical 12 week treatment duration based on the PP population in HCV GT 1, 2, 3, 4, 5 and 6-infected subjects: If this endpoint is statistically significant, then declare the SVR12 endpoint is statistically significant on both PP and ITT population in HCV GT 1, 2, 4, 5 or 6-infected subjects and on the PP population in HCV GT 1 - 6-infected subjects. If not, then announce that SVR12

endpoint is statistically significant based on only the preceding populations and stop testing.

4. Key Secondary 2: Efficacy of the SVR12 rate of 8-week treatment duration compared to the historical 12 week treatment duration based on ITT population in HCV GT 1, 2, 3, 4, 5 or 6-infected subjects: If this endpoint is statistically significant, then declare the SVR12 endpoint is statistically significant on both PP and ITT population in HCV GT 1, 2, 4, 5 or 6-infected subjects and on both the PP and ITT population in HCV GT 1 - 6-infected subjects. If not, then announce that SVR12 endpoint is statistically significant based on only the preceding populations and stop testing.

### **10.3 Primary Efficacy Analysis**

The two primary efficacy analyses included in the fixed-sequence testing procedure as described in Section 10.2 are:

1. Efficacy of the 8-week treatment duration compared to the historical 12-week treatment duration will be demonstrated if the lower bound of the two-sided 95% confidence interval for the percentage of HCV GT 1, 2, 4, 5 or 6-infected subjects based on the PP population in the 8-week treatment duration achieving SVR12 is greater than 94%.
2. Efficacy of the 8-week treatment duration compared to the historical 12-week treatment duration will be demonstrated if the lower bound of the two-sided 95% confidence interval for the percentage of HCV GT 1, 2, 4, 5 or 6-infected subjects based on the ITT population in the 8-week treatment duration achieving SVR12 is greater than 93%.

The two primary efficacy analyses will be tested using the hierarchical order outlined above to control the Type I error rate. Only if success has been demonstrated for the first primary efficacy analysis of SVR12 based on the PP population in HCV GT 1, 2, 4, 5 or

6-infected subjects, will the testing proceed to the second primary efficacy analysis of SVR12 based on the ITT population in HCV GT 1, 2, 4, 5 or 6-infected subjects.

For the first primary efficacy analysis, the PP population (defined in Section 5.1.2) will be used. The PP analysis is used to reduce the risk of bias toward no treatment difference that can occur due to dropouts or other measurement problems, since the subjects excluded in the PP population experience SVR failure for reasons that do not help in discriminating between treatment durations.

For both primary efficacy analyses, the percentage of subjects achieving SVR12 and a two-sided 95% confidence interval will be calculated using the normal approximation to the binomial distribution, unless the number of subjects who failed to achieve SVR12 is less than 5, then the Wilson's score method will be used for the confidence interval instead.

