2. Efficacy of the 8-week treatment duration compared to the historical 12-week treatment duration will be demonstrated if the lower bound of the two-sided 95% confidence interval for the percentage of HCV GT1, 2, 4, 5, and 6-infected subjects in the 8-week treatment duration achieving SVR₁₂ is greater than 93% in the ITT population.

Statistical Methods (Continued):**Efficacy (Continued):**

The two key secondary efficacy analyses included in the fixed-sequence testing procedure are:

1. Efficacy of the 8-week treatment duration compared to the historical 12-week treatment duration will be demonstrated if the lower bound of the two-sided 95% confidence interval for the percentage of HCV GT1, 2, 3, 4, 5, and 6-infected subjects in the 8-week treatment duration achieving SVR₁₂ is greater than 94% in the PP population.
2. Efficacy of the 8-week treatment duration compared to the historical 12-week treatment duration will be demonstrated if the lower bound of the two-sided 95% confidence interval for the percentage of HCV GT1, 2, 3, 4, 5, and 6-infected subjects in the 8-week treatment duration achieving SVR₁₂ is greater than 93% in the ITT population.

The primary and key secondary efficacy analyses will be tested using the hierarchical order outlined above to control the Type I error rate. Only if success has been demonstrated for the first primary efficacy analysis of SVR₁₂ based on the PP population in HCV GT1, 2, 4, 5, and 6-infected subjects will the testing proceed to the second primary efficacy analysis of SVR₁₂ based on the ITT population in HCV GT1, 2, 4, 5, and 6-infected subjects. And only if success has been demonstrated for the second primary efficacy analysis will the testing proceed to the first key secondary efficacy analysis of SVR₁₂ based on the PP population in HCV GT1, 2, 3, 4, 5, and 6-infected subjects, and so on. For all primary and key secondary efficacy analyses, the percentage of subjects achieving SVR₁₂ and a two-sided 95% confidence interval will be calculated using the normal approximation to the binomial distribution, unless the number of subjects who failed to achieve SVR₁₂ is less than 5, then the Wilson's score method will be used for the confidence interval instead.

The other secondary efficacy analyses are listed below and are not included in the fixed-sequence testing:

- The percentage of HCV GT3-infected subjects in the PP population who achieve SVR₁₂;

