8.0 Statistical Methods and Determination of Sample Size

8.1 Statistical and Analytical Plans

Analyses will occur after subjects have completed the PT Week 12 Visit or prematurely discontinued study. The first analysis will occur after all HCV GT1, 2, 4, 5, and 6-infected subjects have completed the PT Week 12 Visit or prematurely discontinued study; the second analysis will occur after all HCV GT3-infected subjects have completed the PT Week 12 Visit or prematurely discontinued study; the third and final analysis will occur after all subjects have completed or prematurely discontinued from the study.

SAS® (SAS Institute, Inc., Cary, NC) for the UNIX operating system will be used for all analyses. All confidence intervals will be two-sided with an alpha level of 0.05.

Descriptive statistics will be provided, such as the number of observations (N), mean, and standard deviation (SD) for continuous variables and counts and percentages for discrete variables.

Safety analyses will be performed on all subjects who receive at least one dose of study drug.

Efficacy analyses will be performed on the intention-to-treat (ITT) population defined as all enrolled subjects who receive at least one dose of study drug, unless otherwise specified. The Per-Protocol (PP) population includes all enrolled subjects who receive at least one dose of study drug, with the exception of subjects who experience breakthrough, or prematurely discontinue treatment prior to Week 8, or have no HCV RNA value in the SVR₁₂ visit window or later.

The primary and key secondary efficacy analyses will be performed on the PP and ITT populations, as specified. The other secondary efficacy analyses will be performed on the ITT population, unless otherwise specified.

Sensitivity analyses of SVR₁₂, when applicable, will be performed on the intention-to-treat population modified to exclude subjects who were enrolled with ineligible genotypes (e.g., GT3 according to phylogenetic analyses for the group of non-GT3-infected subjects) (mITT-GT), and on the mITT-GT population modified to exclude subjects who did not achieve SVR₁₂ for reasons other than virologic failure (mITT-GT-VF).

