8.1.2.1 Primary Efficacy Endpoints

The two primary efficacy analyses are:

1. Efficacy of the 8-week treatment duration compared to the historical 12-week treatment duration will be demonstrated if the lower bound of the two-sided 95% confidence interval for the percentage of HCV GT1, 2, 4, 5, and 6-infected subjects in the 8-week treatment duration achieving SVR₁₂ is greater than 94% in the PP population.
2. Efficacy of the 8-week treatment duration compared to the historical 12-week treatment duration will be demonstrated if the lower bound of the two-sided 95% confidence interval for the percentage of HCV GT1, 2, 4, 5, and 6-infected subjects in the 8-week treatment duration achieving SVR₁₂ is greater than 93% in the ITT population.

The two primary and two key secondary (defined in Section 8.1.2.2.1) efficacy analyses will be performed following a fixed-sequence testing procedure which is described in Section 8.1.2.6.

Only if success has been demonstrated for the first primary efficacy analysis of SVR₁₂ based on the PP population in HCV GT1, 2, 4, 5, and 6-infected subjects will the testing proceed to the second primary efficacy analysis of SVR₁₂ based on the ITT population in HCV GT1, 2, 4, 5, and 6-infected subjects. And only if success has been demonstrated for the second primary efficacy analysis will the testing proceed to the key secondary efficacy analyses described in Section 8.1.2.2.1.

For the first primary efficacy analysis, the PP population will be used. The PP analysis is used to reduce the risk of bias toward no treatment difference that can occur due to dropouts or other measurement problems, since the subjects excluded in the PP population experience SVR failure for reasons that do not help in discriminating between treatment durations.

For both primary efficacy analyses, the percentage of subjects achieving SVR₁₂ and a two-sided 95% confidence interval will be calculated using the normal approximation to the binomial distribution, unless the number of subjects who failed to achieve SVR₁₂ is less than 5, then the Wilson's score method will be used for the confidence interval instead.

A summary of reason for SVR₁₂ non-response (e.g., OTVF, post-treatment relapse, other) will be provided.

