8.2 Determination of Sample Size

It is planned to enroll approximately 330 adult subjects with chronic HCV GT 1 - 6 infection with compensated cirrhosis who are HCV treatment-naïve in the study.

The study was initially designed to enroll about 270 non-GT3-infected subjects and amended to include GT3-infected subjects for a total of 330 GT1 - 6-infected (270 non-GT3 and 60 GT3) subjects.

With approximately 270 subjects with HCV GT1, 2, 4, 5, or 6 infection, this study has approximately 91% power to demonstrate efficacy of the 8-week treatment arm compared to the historical control SVR₁₂ rate (i.e., a two-sided 95% lower confidence bound above 94%) based on Per-Protocol (PP) population, assuming that 98% of the GT1, 2, 4, 5, and 6-infected subjects receiving 8 weeks of treatment in PP population achieve SVR₁₂.

With approximately 270 subjects with HCV GT1, 2, 4, 5, or 6 infection, this study has approximately 82% power to demonstrate efficacy of the 8-week treatment arm compared to the historical control SVR₁₂ rate (i.e., a two-sided 95% lower confidence bound above 93%) based on Intention-to-Treat (ITT) population, assuming that 97% of the GT1, 2, 4, 5, and 6-infected subjects receiving 8 weeks of treatment in ITT population achieve SVR₁₂.

With approximately 330 subjects with HCV GT1 - 6 infection, this study has approximately 90% power to demonstrate efficacy of the 8-week treatment arm compared to the historical control SVR₁₂ rate (i.e., a two-sided 95% lower confidence bound above 94%) based on the PP population, assuming that 98% of the GT1 - 6-infected subjects receiving 8 weeks of treatment in the PP population achieve SVR₁₂.

With approximately 330 subjects with HCV GT1-6 infection, this study has approximately 81% power to demonstrate efficacy of the 8-week treatment arm compared to the historical control SVR₁₂ rate (i.e., a two-sided 95% lower confidence bound above 93%) based on the ITT population, assuming that 97% of the GT1 - 6-infected subjects receiving 8 weeks of treatment in the ITT population achieve SVR₁₂.

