## 10.5 Sensitivity Analyses

The two-sided 95% confidence interval using Wilson's score method will also be calculated, if applicable, as a sensitivity analysis for the primary and key secondary efficacy analyses of SVR12 based on the PP and ITT populations.

The percentage of subjects in the mITT-GT and mITT-GT-VF populations achieving SVR12, as applicable, will be summarized as well as the corresponding two-sided 95% confidence interval using Wilson score's method and the normal approximation to binomial distribution.

Listings of subjects excluded from the mITT-GT, mITT-GT-VF, and PP populations will be provided, as applicable.

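### The success rule rests on the normal-approximation lower bound, so each confirmatory test runs at roughly 3.5% to 6.7% one-sided error against an implied 2.5%; the stated primary power fits a score/Wilson or exact test instead

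*SAP*

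**What the plan says.** Success on each primary analysis requires the lower bound of a two-sided 95% interval to exceed 94% in the PP population or 93% in the ITT population. SAP 10.3 specifies the interval: "two-sided 95% confidence interval will be calculated using the normal approximation to the binomial distribution, unless the number of subjects who failed to achieve"; with fewer than 5 failures, Wilson's score method applies. Protocol 8.1.2.1 has the same rule ("calculated using the normal approximation to the binomial distribution"). SAP 10.4.1 names no interval method for the key secondary tests, but the protocol synopsis extends the rule to them; its sentence begins "For all primary and key secondary efficacy analyses, the percentage of subjects achieving".

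Otherwise Wilson's interval appears for these tests only "as a sensitivity analysis for the primary and key secondary efficacy analyses" (SAP 10.5, and likewise Protocol 8.1.2.3).

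On error control, Protocol 8.1 says: "All confidence intervals will be two-sided with an alpha level of 0.05". SAP 10.2 says: "In order to control the Type I error rate at 0.05, a fixed sequence testing procedure will be used". That sequence covers all four confirmatory tests.

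On power, Protocol 8.2 says that with about 270 subjects "this study has approximately 91% power to demonstrate efficacy of the 8-week treatment arm" on the PP test (true rate 98%), and gives 82% for the ITT test (true rate 97%). It names no calculation method.

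**The concern.** Only the lower bound decides, so a two-sided 95% interval carries an intended one-sided error of 2.5%. The Wald interval is known to be too short on the side that matters when a proportion is close to 1, and here the thresholds are 93% and 94%.

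The trial has no concurrent control. Protocol 5.6.1 and 8.2.1 make the fixed threshold the entire standard of evidence, the PP test gates everything after it, and SAP 4.4.2 says the results are meant to support labeling changes. A regimen lying exactly at the unacceptable rate would pass more often than the interval's nominal level suggests. Two prespecified intervals could also give opposite answers for the same data.

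**Working it through.** **Inputs.** n = 270 (non-GT3) and 330 (GT1-6), thresholds p0 = 94% (PP) and 93% (ITT), and assumed rates p1 = 98% and 97%, all from Protocol 8.2; the interval rule from SAP 10.3 and the synopsis; z = 1.96.

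**1. Reproduce the stated primary power.** A score-type approximation, with the null variance in the critical value, is

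Power = Φ[(p1 − p0 − 1.96·√(p0(1−p0)/n)) / √(p1(1−p1)/n)].

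- PP: (0.04 − 1.96 × 0.01445) / 0.00852 = 1.37, so 91.5% (stated 91%).
- ITT: (0.04 − 1.96 × 0.01553) / 0.01038 = 0.92, so 82.2% (stated 82%).

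The exact binomial power of a Wilson rule is 90.5% and 80.9%. Clopper-Pearson has the same pass limits at n = 270, hence the same power. The rule as written has exact power 97.9% and 93.4%.

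**2. Pass limits under the rule as written, n = 270.** The Wald lower bound is p̂ − 1.96·√(p̂(1−p̂)/n).

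- PP: 10 failures give p̂ = 260/270 and a bound of 94.04% (pass); 11 give 93.57% (fail).
- ITT: 12 failures give 93.10% (pass); 13 give 92.63% (fail).
- Switch: at 4 failures the bounds are 97.08% (Wald) and 96.25% (Wilson). Both are far above either threshold, so the choice of interval below 5 failures cannot alter a decision.

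**3. One-sided error.** This is the exact probability of at most c failures when the true rate equals p0, for each test taken alone.

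| Test | n | Limit c as written | Error | Wilson limit | Error |
|---|---|---|---|---|---|
| Non-GT3 PP, 94% | 270 | 10 | 6.5% | 8 | 1.7% |
| Non-GT3 PP, 94% | 260–268 | 9 | 3.7–4.8% | 8 | 1.8–2.4% |
| Non-GT3 ITT, 93% | 270 | 12 | 5.7% | 10 | 1.6% |
| GT1-6 PP, 94% | 330 | 12 | 3.8% | 11 | 2.1% |
| GT1-6 ITT, 93% | 330 | 15 | 4.4% | 14 | 2.6% |

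Over every n from 255 to 340, the rule as written gives 3.6–6.7% (94% threshold) and 3.5–6.2% (93% threshold). Wilson gives about 1.2–2.6%. If 270 are treated and 1% to 1.7% leave the PP set for non-virologic reasons (an assumed range around the documents' 1% and 1.2%), the average PP error is about 4.2% to 4.6%.

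**4. How often the two planned intervals disagree on the PP gate.** At n = 270 this needs 9 or 10 failures: Wald bounds 94.53% and 94.04%, Wilson 93.79% and 93.32%. The probability is 7.4% at the assumed 98%, 23.0% at a true 97%, and 25.8% at 96.5%; the last two are illustrative PP rates. At n = 260–268 only 9 failures is discordant. The probability at 98% is then the difference in power between the two rules, from 96.19 − 92.01 = 4.2% to 95.49 − 90.80 = 4.7%.

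**The case against.** Several points on the other side stand.

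- **The 6.5% belongs to one n.** The error moves in steps as n changes, and 270 lies just above a step. PP exclusions will probably bring n below 270, to where the error is 3.7% to 4.8%. A reader might infer from the n = 270 figures that the error is generally about 6%, or always more than double the nominal level. The range over n does not support that.
- **The ITT figure ignores the gate.** ITT success counts only after PP success. With true rates of 94% (PP) and 93% (ITT), hence 1 − 0.93/0.94 = 1.06% non-virologic failure, the chance of declaring ITT success with 270 treated is about 3.6%.
- **2.5% is implied, not written.** SAP 10.2 states 0.05, in a passage about multiplicity. At n = 270 both primary tests, taken alone, exceed even 5% one-sided; at a PP n of 260 to 268 the PP test does not. Calling the SAP's statement simply false would go too far.
- **The sizing method is unknown.** It is tempting to say that the trial was sized with Wilson's test. The figures fit a score, Wilson or exact calculation, but no method is named. The 90% and 81% quoted at n = 330 do not reproduce as stand-alone score power (96.9% and 90.8%).
- **Any discordance would be visible.** The rule is prespecified, Wilson's interval is planned beside it, and the normal approximation also appears in the historical results (Protocol Table 2 footnote).

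None of this removes the excess: the stand-alone error is above 2.5% at every n from 255 to 340. A sensitivity analysis shows a disagreement but does not decide the test.

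**Conclusion.** The point holds as an error-rate problem of moderate and n-dependent size: about 3.5% to 6.7% one-sided per test, against the 2.5% implied by the interval. It rests on exact binomial calculations at the thresholds, on n near the planned values, and on reading the two-sided 95% interval as a 2.5% lower-bound test. The ITT and GT1-6 figures are per test, before gating.

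The stated primary power describes a stricter rule than the one written. A reader might infer that the trial is underpowered; the reverse is true, since the written rule passes more easily than Protocol 8.2 suggests. Nor will the Wilson analysis necessarily contradict the primary result. It could do so, in about 7% of trials at n = 270 under the assumed 98%, and more often if the true rate is somewhat lower.

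**What to change.** In SAP 10.3 and 10.4.1, Protocol 8.1.2.1 and the synopsis, make the Wilson score interval the decision interval for all four tests whatever the number of failures. Report the normal-approximation interval as the sensitivity analysis, and adjust SAP 10.5 and Protocol 8.1.2.3 to match. Name the power method in Protocol 8.2.

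Both intervals are already planned, so no extra subjects or data are needed, and exact primary power (90.5% and 80.9%) stays essentially as stated. The change does alter the primary decision rule of an open-label trial in which relapse is reviewed as it proceeds. It should therefore be made by amendment before the first analysis lock, with a record of what outcome data had been seen.

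The cost to the sponsor is a stricter rule: at n = 270 the limits fall from 10 to 8 failures (PP) and from 12 to 10 (ITT). Wilson holds 2.5% only approximately, reaching about 2.6% at some n, including the ITT test at n = 330.
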